## **6.2 Adverse Event Severity**

The investigator will use the following definitions to rate the severity of each adverse event:

- |                 |   |
|-----------------|---|
| Mild     | The adverse event is transient and easily tolerated by the subject.   |
| Moderate | The adverse event causes the subject discomfort and interrupts the subject's usual activities.  |
| Severe   | The adverse event causes considerable interference with the subject's usual activities and may be incapacitating or life-threatening. |

## **6.3 Relationship to Study Drug**

The investigator will use the following definitions to assess the relationship of the adverse event to the use of study drug:

Reasonable Possibility	An adverse event where there is evidence to suggest a causal relationship between the study drug and the adverse event.
No Reasonable Possibility	An adverse event where there is no evidence to suggest a causal relationship between the study drug and the adverse event.

For causality assessments, events assessed as having a reasonable possibility of being related to the study drug will be considered "associated." Events assessed as having no reasonable possibility of being related to study drug will be considered "not associated." In addition, when the investigator has not reported a causality or deemed it not assessable, AbbVie will consider the event associated.

[figure not shown]
If an investigator's opinion of no reasonable possibility of being related to study drug is given, an Other cause of event must be provided by the investigator for the serious adverse event.

#### **6.4 Adverse Event Collection Period**

All serious adverse events, as well as protocol related non-serious adverse events will be collected from the time the subject signed the study-specific informed consent until study drug administration. From the time of study drug administration until 30 days following discontinuation of study drug treatment has elapsed, all adverse events and serious adverse events will be collected, whether solicited or spontaneously reported by the subject. After PT Week 4 until the end of the study only SAE of death will be collected.

Adverse event information will be collected as shown in [Figure 2](#).

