**Table 7. Study Activities (Continued)**

- j. Female subjects with a documented history of bilateral tubal ligation, bilateral oophorectomy or hysterectomy or who are confirmed to be post-menopausal do not require pregnancy testing throughout the trial. A positive urine pregnancy test requires a confirmatory serum test. (Refer to Section 5.3.1.1 [Pregnancy Test] for additional details.) Monthly urine pregnancy testing is required for women of childbearing potential who receive RBV for seven months (or per local RBV label) after end of treatment. Females of childbearing potential that were treated with DAAs only in the Treatment Period should have urine pregnancy testing done through Post-Treatment Week 4.
- k. Urinalysis will not be conducted after the PT Week 4 Visit.
- l. Applies only to subjects with cirrhosis or suspected cirrhosis. The Child-Pugh score will be calculated in the EDC RAVE system. Subjects who were considered to be non-cirrhotic at the Screening Visit but identified as cirrhotic (according to definitions listed in Section 5.1) during the screening period will return to the site prior to the baseline visit for Child-Pugh assessment.
- m. Verify the subject has given consent for the pharmacogenetic sample. If the optional pharmacogenetic sample is not collected on Study Day 1, it may be collected at any other visit during the study.
- n. For subjects with compensated cirrhosis:
- Subjects receiving 12 weeks of treatment will have a liver ultrasound performed at the screening visit and all PT visits except PT Week 4.
  - Subjects receiving 24 weeks of treatment will have a liver ultrasound performed at the screening visit, Week 24 Visit, and all PT visits except the PT Week 4 and PT Week 12.
- For subjects without cirrhosis:
- Liver ultrasound will be performed at the screening visit, PT Week 52, PT Week 156 and PT Week 260.
- Subjects with a historical negative liver ultrasound, CT or MRI (within 3 months prior to screening) are not required to undergo a screening ultrasound.
- o. The DDI tool provided by the sponsor should be utilized to evaluate the concomitant medications.
- p. AE and concomitant medications will not be collected after the PT Week 4 Visit. Only anti-HCV medications and concomitant medications relevant to SAE of death will be collected after the PT Week 4 Visit.
- q. SF-36v2 and FACIT-F should be administered as the first study procedure at each visit and in the order listed.

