## **6.6 Pregnancy**

Subjects and their partners should avoid pregnancy and males should avoid sperm donation throughout the course of the study, starting with Study Day 1 and for 30 days after the end of treatment with DAAs only, or for 7 months after the last dose of RBV (or per local RBV label) and/or consistent with local treatment guidelines for RBV.

Pregnancy in a study subject must be reported to the AbbVie within 1 working day of the site becoming aware of the pregnancy. Subjects who report a positive pregnancy test during the Treatment Period must be notified to stop RBV (if applicable) immediately. Administration of DAAs may be continued at the investigator's discretion after discussion with the subject, if the benefit of continuing therapy is felt to outweigh the risk (Section 5.4.1).

Information regarding a pregnancy occurrence in a study subject and the outcome of the pregnancy will be collected for pregnancies occurring up to 30 days after the end of treatment with DAAs only, or 7 months (or per local RBV label) after the last dose of RBV for treatment with DAAs plus RBV. The investigator is encouraged to report the pregnancy information to the voluntary RBV Pregnancy Registry, if RBV is included within the regimen.

Subjects who discontinue study medications due to pregnancy will be monitored for SVR in the Post-Treatment Period as described in Section 5.1.

Pregnancy in a study subject is not considered an adverse event. However, the medical outcome of an elective or spontaneous abortion, stillbirth or congenital anomaly is considered a serious adverse event and must be reported to the Sponsor within 24 hours of the site becoming aware of the event.

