11.2.2 Listing of Adverse Event

Listings of all serious adverse events (from the time the subject signed the study-specific informed consent until the end of the study), treatment-emergent serious adverse events, treatment-emergent adverse events leading to death, treatment-emergent adverse events leading to discontinuation of study drug, treatment-emergent adverse events leading to study drug interruptions, treatment-emergent adverse events leading to RBV dose modifications, and treatment-emergent adverse events of special interest will be provided.

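### Protocol 6.4 limits SAE collection after PT Week 4 to deaths, while 6.6 requires pregnancy outcomes to be reported as SAEs with no such limit; the two sections need reconciling

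*Protocol*

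**What the plan says.** **Collection rules.** Under Protocol 6.4, from first dose "until 30 days following discontinuation of study drug treatment has elapsed, all adverse events and serious adverse events will be collected". For the rest of the study it says: "After PT Week 4 until the end of the study only SAE of death will be collected". Table 7 footnote p states: "AE and concomitant medications will not be collected after the PT Week 4 Visit". Neither place makes an exception for pregnancy or refers to 6.6.

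**Pregnancy rules.** Protocol 6.6 says: "Information regarding a pregnancy occurrence in a study subject and the outcome of the pregnancy will be collected". For ribavirin-treated subjects this covers pregnancies arising up to 7 months after the last ribavirin dose, or as the local ribavirin label sets; for subjects on DAAs alone it covers 30 days after treatment. Pregnancy itself is not an adverse event, but "the medical outcome of an elective or spontaneous abortion, stillbirth or congenital anomaly is considered a serious adverse event", and it "must be reported to the Sponsor within 24 hours of the site becoming aware of the event". Section 6.1.2 separately places congenital anomaly, abortion and stillbirth within the SAE criteria.

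**Analysis.** SAP 11.2.1 ends the treatment-emergent period 30 days after the last dose. SAP 11.2.2 plans a listing of every SAE from consent to the end of the study.

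**The concern.** Section 6.4 is where a site looks to learn which SAEs to record and for how long. Its wording after PT Week 4 is exclusive: deaths and nothing else. Section 6.6 creates a second class of SAE whose members can arise many months after that cut-off. A site that applies 6.4 literally would not collect an SAE that 6.6 obliges it to send within 24 hours.

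The protocol gives the known teratogenicity of ribavirin as a reason for its contraception criteria (rationale under 5.2.1), so these outcomes matter to the safety record. Two things are exposed: prompt reporting to the sponsor, and the completeness of the SAP 11.2.2 listing. Among the SAP's planned adverse event outputs, that listing is the only one that would show a pregnancy-outcome SAE with onset more than 30 days after the last dose.

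**Working it through.** The documents give no figure to reproduce. The check has two parts: reading the rules side by side, and working out when pregnancy outcomes would occur.

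**1. The rules side by side**

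| Question | 6.4 | Table 7 footnote p | 6.6 |
|---|---|---|---|
| What is collected after PT Week 4? | SAE of death only | No AEs | Pregnancy occurrence and outcome |
| Is an anomaly, abortion or stillbirth after PT Week 4 covered? | No, by its wording | Not mentioned | Yes: SAE, 24 hours from awareness |
| Is there a time limit on reporting the outcome? | PT Week 4 | PT Week 4 visit | None stated |
| Is there a cross-reference between the rules? | None to 6.6 | None to 6.6 | None to 6.4 |

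Footnote p is weaker evidence than 6.4. Its mention of death limits which concomitant medications are recorded later, not which SAEs. Read literally it would also bar death reports, which 6.4 and footnote t require. It is shorthand, and the direct conflict is between 6.4 and 6.6.

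**2. Timing**

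Inputs from the protocol:
- Treatment length T = 12 or 24 weeks (Table 5).
- Cut-off at PT Week 4 (6.4).
- Ribavirin pregnancy window W = 7 months = 7 × 30.4375 / 7 = 30.4 weeks (6.6).

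Assumptions not in the documents:
- About 38 weeks from conception to term.
- 2 to 12 weeks from conception to an early loss.
- For the shares below, conception spread evenly from Day 1 to the end of the window.

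*Term births.* Earliest PT week = 38 − T.
- 24 weeks of treatment: 38 − 24 = PT Week 14.
- 12 weeks of treatment: 38 − 12 = PT Week 26.

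Stopping treatment early moves these to later PT weeks. At the other end, conception at month 7 gives a term birth at 30.4 + 38 = 68.4 weeks, about 16 months after the last dose. More generally, any outcome more than T + 4 weeks after conception (28 or 16 weeks) falls beyond the cut-off, even for conception on Day 1.

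*Early losses.* With lag L from conception to loss, the share after PT Week 4 is [W − max(−T, 4 − L)] / (W + T), set to 0 if negative.

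| Case | L = 2 weeks | L = 12 weeks |
|---|---|---|
| Ribavirin window, T = 12 | 28.4 / 42.4 = 67% | 38.4 / 42.4 = 91% |
| Ribavirin window, T = 24 | 28.4 / 54.4 = 52% | 38.4 / 54.4 = 71% |
| Conceived on treatment (W = 0), T = 12 | 0% | 8 / 12 = 67% |
| Conceived on treatment (W = 0), T = 24 | 0% | 8 / 24 = 33% |

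All term births fall after the cut-off. Early losses range from none to about nine in ten, depending on when conception occurs and how long the pregnancy lasts.

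**The case against.** The strongest reply is that sites must follow the whole protocol, and 6.6 is the specific rule. It requires a subject's pregnancy to be notified within 1 working day, collects the outcome, and sets a 24-hour duty with no end date. Section 6.5 sets no end date for SAE reporting either. Pregnancy also stays in view after PT Week 4: Table 7 footnote j and section 5.3.1.1 require monthly urine tests for seven months after ribavirin (or per local label), with serum confirmation of a positive result. A site could end routine collection at PT Week 4 and still report pregnancy outcomes through 6.6.

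Most of this stands, and it limits the point. A reader might infer that a birth defect after ribavirin exposure would go unreported; 6.6 does not support that. A reader might also infer that nearly all pregnancy outcomes fall after the cut-off; that is right for term births but not for early losses. Nor do the documents make pregnancy outcomes the only serious harm tied to ribavirin, since 6.7.4 describes hemoglobin decreases as a well characterized effect.

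What the reply does not remove is the exclusive wording of 6.4. Nothing in the text says that 6.6 overrides it. Two sources cannot be checked: Figure 2, to which 6.4 refers, is not reproduced, and the eCRF completion instructions are not among the documents. An exception in either would help sites but would leave the text of 6.4 as it is.

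**Conclusion.** The inconsistency is real and should be corrected. Read literally, 6.4 excludes every pregnancy-outcome SAE after PT Week 4, while 6.6 makes those same events reportable within 24 hours. The excluded set contains all term births and between 0% and 91% of early losses across the cases worked above. These figures rest on about 38 weeks to term, 2 to 12 weeks to an early loss, evenly spread conception, and treatment of the nominal length without breaks.

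The consequence is a risk of under-reporting and of gaps in the SAP 11.2.2 listing. It is not certain non-reporting, because the duty in 6.6 remains in force. The documents give no expected number of pregnancies, so the number of events at risk cannot be estimated; it may well be small. No efficacy analysis is affected.

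**What to change.** Reword the last collection rule in 6.4 along these lines: 'From PT Week 4 to the end of the study, SAE collection is limited to deaths and to pregnancy-outcome SAEs reportable under Section 6.6.' Add the same cross-reference to Table 7 footnote p. If Figure 2 or the eCRF completion instructions repeat the death-only rule, align them too. SAP 11.2.2 needs no change, since its listing already runs to the end of the study.

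This adds no new duty, because 6.6 already imposes it. The cost is a protocol clarification and a few extra SAE forms at most.

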**Figure 2. Adverse Event Collection**

## 6.5 Adverse Event Reporting

In the event of a SAE, whether associated with study drug or not, the Investigator will notify Clinical Pharmacovigilance within 24 hours of the site being made aware of the SAE by entering the SAE data into the electronic data capture (EDC) system. For SAEs that occur prior to the site having access to the RAVE® system, or if RAVE is not operable, the forms should be faxed to Clinical Pharmacovigilance within 24 hours of the site being made aware of the SAE.

**[contact]**

The sponsor will be responsible for Suspected Unexpected Serious Adverse Reactions (SUSAR) reporting for the Investigational Medicinal Product (IMP) in accordance with Directive 2001/20/EC. The reference document used for DAA SUSAR reporting in the EU countries will be the most current version of the Investigator's Brochure. The reference document used for RBV SUSAR reporting in the EU countries will be the most current version of the Summary of Product Characteristics (SmPC).

## **6.6 Pregnancy**

Subjects and their partners should avoid pregnancy and males should avoid sperm donation throughout the course of the study, starting with Study Day 1 and for 30 days after the end of treatment with DAAs only, or for 7 months after the last dose of RBV (or per local RBV label) and/or consistent with local treatment guidelines for RBV.

Pregnancy in a study subject must be reported to the AbbVie within 1 working day of the site becoming aware of the pregnancy. Subjects who report a positive pregnancy test during the Treatment Period must be notified to stop RBV (if applicable) immediately. Administration of DAAs may be continued at the investigator's discretion after discussion with the subject, if the benefit of continuing therapy is felt to outweigh the risk (Section 5.4.1).

Information regarding a pregnancy occurrence in a study subject and the outcome of the pregnancy will be collected for pregnancies occurring up to 30 days after the end of treatment with DAAs only, or 7 months (or per local RBV label) after the last dose of RBV for treatment with DAAs plus RBV. The investigator is encouraged to report the pregnancy information to the voluntary RBV Pregnancy Registry, if RBV is included within the regimen.

Subjects who discontinue study medications due to pregnancy will be monitored for SVR in the Post-Treatment Period as described in Section 5.1.

Pregnancy in a study subject is not considered an adverse event. However, the medical outcome of an elective or spontaneous abortion, stillbirth or congenital anomaly is considered a serious adverse event and must be reported to the Sponsor within 24 hours of the site becoming aware of the event.

## **6.7 Toxicity Management**

For the purpose of medical management, all adverse events and laboratory abnormalities that occur during the study must be evaluated by the investigator. A table of Clinical Toxicity Grades for evaluating laboratory abnormalities is provided in [Appendix C](#). This table should be used in determination of the appropriate toxicity management as discussed in Sections 6.7.1 through 6.7.5.

A drug-related toxicity is an adverse event or laboratory value outside of the reference range that is judged by the investigator or the Sponsor as having a "reasonable possibility" of being related to the study drug (Section 6.3). A toxicity is deemed "clinically

significant" based on the medical judgment of the investigator. Laboratory abnormalities will be managed as deemed clinically appropriate by the investigator until resolved.

Investigators should avoid interrupting study drugs for more than 7 consecutive days. The Investigator should ensure that any study drug interruptions or RBV dose modifications and associated adverse events are promptly entered into the appropriate eCRFs.

The toxicity management guidelines below should be followed throughout the Treatment Period of the study.

### **6.7.1 Grade 1 or 2 Laboratory Abnormalities and Mild or Moderate Adverse Events**

Subjects who develop a mild or moderate adverse event or Grade 1 or 2 laboratory abnormality, other than those discussed separately in Section 6.7.4 (Management of Decreases in Hemoglobin) for subjects receiving RBV, Section 6.7.5 (Management of ALT Elevations) and Section 6.7.6 (Creatinine Clearance), may continue study drugs with follow-up per study protocol and in accordance with local standard of care.

### **6.7.2 Grade 3 or 4 Laboratory Abnormalities**

With the exception of grade 3 or higher abnormalities of total bilirubin, uric acid, phosphorus, total cholesterol, triglycerides, or glucose (in subjects with a history of diabetes), if a subject experiences a grade 3 or greater abnormal laboratory parameter during the Treatment Period, the abnormal laboratory test should be repeated. If the grade 3 or greater abnormality is confirmed, the investigator should assess whether the abnormality can be managed medically without interruption of study drug, or whether study drugs should be interrupted and the laboratory parameter followed until it improves. If study drugs are interrupted and restarted and the abnormality recurs, then study drugs should be permanently discontinued.

Decreases in serum hemoglobin or in calculated creatinine clearance for subjects receiving RBV or elevations of serum ALT should be managed according to the guidance in Section 6.7.4, Section 6.7.5 and Section 6.7.6 below. Grade 3 or greater abnormalities

of total bilirubin, uric acid, phosphorus, total cholesterol, triglycerides or glucose (in subjects with a history of diabetes) should be managed medically as appropriate and do not require confirmation or study drug interruption, unless deemed necessary by the investigator.

### **6.7.3 Severe Adverse Events or Serious Adverse Events**

If a subject experiences a severe adverse event or a serious adverse event that the investigator considers to have a reasonable possibility of relationship to study drug, the investigator should assess whether the adverse event can be managed medically without interruption of study drug, or whether study drugs should be interrupted until it improves. If study drugs are interrupted and restarted and the adverse event recurs, then study drugs should be permanently discontinued.

If a subject experiences a severe adverse event or serious adverse event that is considered unrelated (no reasonable possibility) to the study drugs, it is not necessary to interrupt study drugs unless an interruption is required because of the nature of the event (e.g., unable to take oral medications).

The investigator should ensure that all serious adverse events are reported to AbbVie within 24 hours of awareness. Serious adverse event follow-up information, including associated dose interruptions (or discontinuations), must be reported to AbbVie within 24 hours of awareness by entering updated SAE information into the appropriate eCRFs.

Severe adverse events and any associated dose interruptions (or discontinuations) should be entered into the appropriate eCRFs.

### **6.7.4 Management of Decreases in Hemoglobin**

#### **For subjects not receiving ribavirin:**

Hemoglobin decreases should be managed according to grade based on the guidance in Section 6.7.1 – Section 6.7.2 above.

**For subjects receiving ribavirin:**

Reductions in hemoglobin are a well characterized side effect of RBV exposure. If a subject receiving the standard dose of RBV experiences a hemoglobin decrease meeting one of the criteria outlined in [Table 12](#), a confirmatory test should be performed. If the hemoglobin decrease is confirmed, the management guidelines in [Table 12](#) should be followed. Management will be different for subjects without a history of known cardiac disease and subjects with known cardiac disease. Subjects experiencing decreases in hemoglobin that do not meet the criteria outlined in [Table 12](#) may need hemoglobin evaluations at more frequent intervals at the discretion of the investigator.

The dose of RBV should not be further modified in subjects with creatinine clearance < 50 mL/min who are receiving a reduced dose of RBV. Reductions in hemoglobin in these subjects should be managed as medically appropriate and as outlined in [Table 12](#).

Use of hematologic growth factors (such as erythropoietin or filgrastim) or blood transfusions are permitted at the discretion of the investigator. Management of hematologic growth factor therapy is the responsibility of the Investigator, and growth factors will not be provided by AbbVie.

Alternate management of hemoglobin decreases outside of these criteria is permitted with approval of the AbbVie Study Designated Physician.

**Table 12. Ribavirin Dose Modification Guidelines in Management of Hemoglobin Decreases**

Hemoglobin Value	Intervention
Subjects with creatinine clearance <math>\geq</math> 50 mL/min	
< 10 g/dL and $\geq$ 8.5 g/dL	Reduce RBV dose.* Study drugs may be continued. If hemoglobin increases to $\geq$ 10 g/dL, may increase RBV; with gradual dose increases in 200 mg increments towards original dose.
< 8.5 g/dL	Interrupt RBV. Manage the subject as medically appropriate. If hemoglobin increases to $\geq$ 8.5 g/dL, RBV may be restarted.
Additional guidance for subjects with history of stable cardiac disease and creatinine clearance <math>\geq</math> 50 mL/min	
Hemoglobin decrease of $\geq$ 2 g/dL during any 4-week treatment period	Reduce RBV dose.* If a subsequent hemoglobin result is greater than the level that triggered the dose reduction, RBV dose may be increased; with gradual dose increases in 200 mg increments.
< 12 g/dL after a 4-week RBV dose reduction	Interrupt RBV. Manage the subject as medically appropriate. If hemoglobin increases to $\geq$ 12 g/dL RBV may be restarted.
For subjects with creatinine clearance < 50 mL/min	
< 10 g/dL	Interrupt RBV. Manage the subject as medically appropriate. If hemoglobin increases to $\geq$ 10 g/dL, RBV may be restarted. If creatinine clearance increases to $\geq$ 50 mL/min, refer to guidance above.

\* 1st dose reduction of RBV is by 200 mg/day or per local label. If needed, 2nd dose reduction of RBV is by an additional 200 mg/day. Subjects whose dose of RBV is reduced to 600 mg daily receive one 200 mg tablet in the morning and two 200 mg tablets in the evening.

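### For cardiac subjects, Table 12 permits a ribavirin increase at some hemoglobin values where its next row directs interruption, and does not say which row governs

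*Protocol*

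**What the plan says.** Protocol Section 6.7.4 covers hemoglobin decreases in subjects who receive ribavirin. A value that meets a Table 12 criterion is to be repeated, and "If the hemoglobin decrease is confirmed, the management guidelines in" Table 12 then apply. The section ends with a release clause: "Alternate management of hemoglobin decreases outside of these criteria is permitted with approval of the AbbVie Study Designated Physician".

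One block of Table 12 is headed "Additional guidance for subjects with history of stable cardiac disease and creatinine clearance" of at least 50 mL/min. It has two rows.

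- **Row 1.** The entry condition is "Hemoglobin decrease of $\geq$ 2 g/dL during any 4-week treatment period". The action is to reduce ribavirin. The row continues: "If a subsequent hemoglobin result is greater than the level that triggered the dose reduction, RBV dose may be increased", in gradual 200 mg steps.
- **Row 2.** The entry condition is "< 12 g/dL after a 4-week RBV dose reduction". The action is: "Interrupt RBV. Manage the subject as medically appropriate. If hemoglobin increases to $\geq$ 12 g/dL RBV may be restarted".

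The table footnote describes the size of the dose reductions. Neither the footnote, the table nor the text of Section 6.7.4 gives an order of precedence between the two rows.

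**The concern.** Row 1 ties re-escalation to a relative level, the value that triggered the reduction. It has no absolute floor and no time limit. Row 2 ties interruption and restart to a fixed level of 12 g/dL and makes no exception for a subject whose hemoglobin has risen above the trigger. Both rows apply to the same subjects, so one result can satisfy both.

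What is at stake is consistent safety management in a group for which the protocol adds anemia guidance of its own. A site that looks to row 1 finds express permission to raise the dose at a value where row 2 directs that ribavirin be interrupted. There is also a small reporting effect. SAP Section 8.0 counts ribavirin modifications due to a hemoglobin decrease, and counts modifications to 0 mg separately, so the row applied would affect those counts.

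**Working it through.** The plan gives no figure on this point to reproduce. The check is a comparison of the two conditions.

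**Notation.** P is hemoglobin before the fall, T the value that triggered the reduction, and H the value after 4 weeks at the reduced dose, all in g/dL.

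**Inputs from Table 12**
- Reduction: P − T ≥ 2 within 4 weeks.
- Row 1 permits an increase if H > T.
- Row 2 directs interruption if H < 12.

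**Step 1: the overlap.** Both rows are met exactly when T < H < 12. This requires T < 12. Before 4 weeks at the reduced dose, only row 1 can apply.

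**Step 2: when T falls below 12.** Since T ≤ P − 2, any P below 14.0 gives T < 12. For P of 14.0 or more, the fall must exceed P − 12: more than 2.0 from 14.0, or more than 2.5 from 14.5.

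**Step 3: cases**

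| P | T | Fall | H | Row 1 permits increase (H > T) | Row 2 directs interruption (H < 12) |
|---|---|---|---|---|---|
| 14.0 | 11.5 | 2.5 | 11.8 | yes | yes |
| 13.5 | 11.0 | 2.5 | 11.5 | yes | yes |
| 13.0 | 11.0 | 2.0 | 11.8 | yes | yes |
| 12.8 | 10.5 | 2.3 | 11.2 | yes | yes |
| 14.5 | 12.5 | 2.0 | 13.0 | yes | no |
| 14.5 | 12.5 | 2.0 | 11.8 | no | yes |

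The last two cases show that the rows do not conflict when T is 12 or above.

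**Step 4: the overlap on a grid.** All combinations in steps of 0.1 g/dL were listed, with P from 12.0 to 17.0, T ≤ P − 2, H ≤ P, and T and H at least 10.0 so that the general rows below 10 g/dL stay out of play. The range for P is an assumption: entry requires hemoglobin at or above the lower limit of normal, but the protocol gives no value for that limit. Of 72,046 combinations, 8,550 meet both rows, 40,070 row 1 only, 17,970 row 2 only and 5,456 neither. This shows that the overlap is not a single edge value. It does not estimate how often subjects would fall in it.

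**Step 5: the visit schedule.** Protocol Table 7 schedules on-treatment hematology at Day 1, Weeks 2, 4 and 12, and end of treatment.
- Weeks 4 and 12 are 8 weeks apart, so scheduled results can show a fall within 4 weeks only at Week 2 or Week 4.
- Four weeks of reduced dose then end at Week 6 or Week 8 (2 + 4 or 4 + 4), if the reduction starts at that visit. The next scheduled result is Week 12.
- In a 12-week regimen, Week 12 is the end of treatment. In a 24-week regimen, 24 − 12 = 12 weeks of ribavirin remain.
- Other tests can bring the overlap forward. Section 6.7.4 calls for confirmatory tests, and Section 5.1.2 allows unscheduled visits.

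**The case against.** The strongest reply is that the rows differ in force. Row 1 says the dose may be increased; row 2 says to interrupt. An investigator who interrupts at 11.8 g/dL breaks neither row. The rows can also be read in sequence, with row 1 as the first step and row 2 as the narrower rule after 4 weeks. This stands in part. A reader might infer that the rows order opposite actions, so that two sites could each comply while one raises the dose and the other stops it. The documents do not support that: the site that raises the dose has not followed row 2. But the sequential reading is one the reader must supply, and row 1's permission carries no limit that would end it at 4 weeks.

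The second reply is that Table 12 is guidance and that the release clause lets the sponsor's physician agree to other management. So interruption should not be called mandatory without qualification. The clause does not settle the overlap, however. It concerns management outside the criteria, and an investigator who uses row 1's permission would see that as acting within them. Nothing prompts a call to the sponsor.

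The third reply is that the situation is narrow, and it is. Step 5 of the working largely confines it to 24-week subjects and to unscheduled tests, and subjects with genotype 1b without cirrhosis receive no ribavirin. On the other side, Table 5 now makes 24 weeks with ribavirin the default for genotype 1a with cirrhosis. In protocol Table 3, hemoglobin below 10 g/dL occurred in 11.0% of the 24-week cirrhotic arm against 7.2% of the 12-week arm. Those figures suggest that the hemoglobin rules will be used. They say nothing about how often this overlap occurs.

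A reader might also see a second conflict in the general rows at 8.5 to below 10 g/dL, where ribavirin may be restarted after an interruption with no dose named, while the row above calls for a reduced dose. Those rows can be read together: one says when restart is allowed, the other covers the dose in that band. They do not contradict each other.

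**Conclusion.** The point holds as an unresolved overlap in a safety table. For subjects with stable cardiac disease and creatinine clearance of at least 50 mL/min, every value after 4 weeks at the reduced dose that lies above the trigger and below 12 g/dL meets both the permission to increase and the direction to interrupt. A fall of at least 2 g/dL from any starting value below 14.0 g/dL puts the trigger in the range where this can happen.

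How many subjects are affected cannot be derived, because the documents give neither the number of cardiac subjects nor the distribution of hemoglobin changes. The reach is limited by the visit schedule and by the difference in force between the rows.

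A reader might go further and infer an effect on SVR12 or on the primary comparison. The documents do not support that: no efficacy analysis in SAP Section 10 names ribavirin modification, and the reporting effect identified here is on the descriptive counts in SAP Section 8.0. Nor do the documents rank cardiac subjects as those most at risk from anemia; Section 6.7.4 says only that their management differs. The correction is worth making at the next amendment because the text is a safety instruction.

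**What to change.** Reconcile the two cardiac rows of Table 12 so that one hemoglobin value leads to one action. Either state which row governs when both are met, or word the re-escalation condition and the interruption and restart condition so that they cannot hold together. Which clinical rule stands is for the sponsor's clinical team to decide.

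The cost is a wording change to Table 12 in the next amendment. The present amendment already edits that table's footnote. No visits, procedures or subjects are added, and the SAP needs no change.
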